10.6. Appendix 6: Abbreviations

The following is a list of abbreviations that may be used in the protocol.

Abbreviation	Term
Abs	absolute
AD	atopic dermatitis
ADSI	atopic dermatitis severity index
AE	adverse event
ALT	alanine aminotransferase
AST	aspartate aminotransferase
AUC	area under the curve
β -hCG	beta-human chorionic gonadotropin
BID	twice daily
BPO	benzoyl peroxide
BSA	body surface area
BUN	blood urea nitrogen
cAMP	cyclic adenosine monophosphate
CFR	Code of Federal Regulations
CIOMS	Council for International Organizations of Medical Sciences
CK	creatin kinase
C_{max}	maximum observed concentration
CO ₂	carbon dioxide (bicarbonate)
CONSORT	Consolidated Standards of Reporting Trials
CRF	case report form
CRO	contract research organization
CSR	clinical study report
CT	clinical trial
DILI	drug-induced liver injury
DMC	data monitoring committee
DU	dispensable unit
EC	ethics committee
EC ₅₀	half maximal effective concentration
ECG	Electrocardiogram
eCRF	electronic case report form
EDP	exposure during pregnancy
EMA	European Medicines Agency
EU	European Union
EudraCT	European Clinical Trials Database
FAS	Full Analysis Set
FSH	follicle-stimulating hormone
GCP	Good Clinical Practice
GGT	gamma-glutamyl transferase
HIPAA	Health Insurance Portability and Accountability Act

Abbreviation	Term
HRQoL	health related quality of life measures
HRT	hormone replacement therapy
IB	investigator's brochure
ICD	informed consent document
ICH	International Council for Harmonisation
ID	Identification
IMP	investigational medicinal product
IND	investigational new drug application
INR	international normalized ratio
IP manual	investigational product manual
IRB	institutional review board
IRT	interactive response technology
ISGA	investigator's static global assessment
IUD	intrauterine device
IUS	Intrauterine hormone-releasing system
IWR	interactive Web-based response
LFT	liver function test
MAR	missing at random
MMRM	mixed effect models for repeated measures
MUSE	maximal use systemic exposure
N/A	not applicable
NbUVB	narrow band ultraviolet B
NIMP	noninvestigational medicinal product
NRS	numerical rating scale
PCD	primary completion date
PD	pharmacodynamic(s)
PDE-4	phosphodiesterase-4
PI	principal investigator
PK	pharmacokinetic(s)
PKA	protein kinase A
PMA	phorbol 12-myristate 13-acetate
PPAS	Per-Protocol Analysis Set
PRN	pro re nata
PT	prothrombin time
PUVA	psoralen plus ultraviolet A
QD	once daily
qual	Qualitative
RBC	red blood cell
RIPT	repeat-insult patch test
SAE	serious adverse event
SAP	statistical analysis plan
SoA	schedule of activities

Abbreviation	Term
SOP	standard operating procedure
SRSD	single reference safety document
SUSAR	suspected unexpected serious adverse reaction
TBili	total bilirubin
TEAE	treatment-emergent adverse event
T _{max}	time to reach maximum observed plasma concentration
TQT	thorough QT
TSS	Total Sign Score
ULN	upper limit of normal
US	United States
WBC	white blood cell
WOCBP	woman of childbearing potential
%BSA	percent of body surface area

## 1. VERSION HISTORY

**Table 1. Summary of Changes**

Version/ Date	Associated Protocol Amendment	Rationale	Specific Changes
1 6 Jun 2019	Original 22 Feb 2019	Not Applicable	Not Applicable
2 19 Dec 2019	Original 22 Feb 2019	3.4 The baseline data of “Duration of disease (in years)” was not collected.	3.4 “Duration of disease (in years)” was deleted.
		Appendix 2 The visit windows for analysis were not described.	Appendix 2 The visit windows for efficacy variables which were same as study C3291001 were added.

## 2. INTRODUCTION

This statistical analysis plan (SAP) provides the detailed methodology for summary and statistical analyses of the data collected in Study C3291028. This document may modify the plans outlined in the protocol; however, any major modifications of the primary endpoint definition or its analysis will also be reflected in a protocol amendment.

### 2.1. Study Objectives, Endpoints, and Estimands

Objectives	Endpoints	Estimands
Primary:	Primary:	Primary:

 
To compare the efficacy of crisaborole ointment 2%, administered once daily (QD) or twice daily (BID) relative to the corresponding vehicle (QD or BID), on Total Sign Score (TSS) assessment in target lesions, in the treatment of mild to
 
	
 
Change from baseline in TSS in target lesions treated with crisaborole ointment or vehicle on Day 15 in each regimen (regimen 1: QD,
 
	
 
This estimand is the hypothetical estimand, which estimates the effect as if all participants maintain their randomized treatment.
 
Population: Participants with mild to moderate AD in adults (cohort 1) and
 

Objectives	Endpoints	Estimands

moderate atopic dermatitis (AD) in adults (cohort 1) and pediatrics (cohort 2).
	
regimen 2: BID) for each cohort.
	
pediatrics (cohort 2) as defined by the inclusion and exclusion criteria and are randomized and received at least one of the investigational products.
 
 
• Intercurrent event: All efficacy data after discontinuation of treatment will not be considered.
 
• Population-level summary: Least-square means of intra-participant difference between crisaborole ointment 2% vs corresponding vehicle in each regimen for each cohort and pooled cohort.
 

Secondary:	Secondary:	Secondary:

 
• To evaluate the efficacy of crisaborole ointment 2% BID relative to crisaborole ointment 2% QD, on TSS assessment in target lesions, in the treatment of mild to moderate AD in adults (cohort 1) and pediatrics (cohort 2).
 
	
 
• Change from baseline in TSS in target lesions treated with crisaborole ointment or vehicle on Day 15 in each regimen for each cohort.
 
	
 
• This estimand is the hypothetical estimand, which estimates the effect as if all participants maintain their randomized treatment.
 
• Population: Participants with mild to moderate AD in adults (cohort 1) and pediatrics (cohort 2) as defined by the inclusion and exclusion criteria and are
 

Objectives	Endpoints	Estimands
		
randomized and received at least one of the investigational products;
 
 
• Intercurrent event: All efficacy data after discontinuation of treatment will not be considered.
 
• Population-level summary: Difference in least square means between crisaborole ointment 2% BID and crisaborole ointment 2% QD for each cohort and pooled cohort.
 

 
• To evaluate the efficacy of crisaborole ointment 2%, administered QD or BID, on TSS, ISGA and Pruritus assessments in target lesions, in the treatment of mild to moderate AD in adults (cohort 1) and pediatrics (cohort 2).
 
	
 
• Change from baseline in TSS in target lesions treated with crisaborole ointment or vehicle on Day 8 in each regimen for each cohort.
 
• Change from baseline in ISGA in target lesions treated with crisaborole ointment or vehicle at each visit up to Day 15 in each regimen for each cohort.
 
• Change from baseline in
 
	
 
• The other secondary efficacy endpoints will be analyzed using the estimands described above.
 

Objectives	Endpoints	Estimands
	
pruritus assessments in target lesions treated with crisaborole ointment or vehicle at each day up to Day 15 in each regimen using following scales;
 
Cohort 1: Peak Pruritus numerical rating scale (NRS) (age ≥12)
 
Cohort 2: Itch Severity Scale (age 6-11)
 
Cohort 2: Caregiver Reported Itch Severity NRS (age 2-11).
	

 
To assess the safety and local tolerability of crisaborole ointment 2%, administered QD or BID, in the treatment of mild to moderate AD in adults (cohort 1) and pediatrics (cohort 2)
 
	
 
Incidence of treatment emergent adverse events (TEAEs) and serious adverse events (SAEs) in each regimen for each cohort.
 
	
 
There is no defined estimand for these endpoints and they will be analyzed descriptively.
 

CCI [REDACTED]
	
[REDACTED]
	
[REDACTED]

[REDACTED]
	
[REDACTED]
	
[REDACTED]

Objectives	Endpoints	Estimands

CCI [REDACTED]
	
[REDACTED]
	
[REDACTED]

## 2.2. Study Design

This is a Phase 2b, multi-center, randomized, double-blind, vehicle-controlled, intra-participant study to evaluate efficacy and safety of two regimens of crisaborole ointment 2% in Japanese pediatric and adult participants (cohort 1: 12 years and older, cohort 2: 2 to under 12 years old) with mild to moderate AD. After completing screening activities, including meeting eligibility criteria, two target lesions with same severity will be determined by the investigator, participants will be randomized to one of the regimens, QD or BID (randomization ratio; 1:1), and crisaborole ointment 2% or vehicle will be randomly assigned to each target lesion at Baseline/Day 1. Both target lesions are to be treated at the same assigned dosing regimen and dosing regimen is unblinded information to sponsor, investigators/study sites and participants. Participants will be treated with investigational products administered for 2 weeks and followed-up 28 days after the end of treatment.

Cohort	Regimen	Investigational Products	N	Study Treatment
Cohort 1 a	Regimen 1	Crisaborole ointment 2% QD vs Vehicle QD	20	Participants will visit the site once daily to be administered investigational products by site staff.
	Regimen 2	Crisaborole ointment 2% BID vs Vehicle BID	20	Participants will visit the site twice daily to be administered investigational products by site staff.
Cohort 2 b	Regimen 1	Crisaborole ointment 2% QD vs Vehicle QD	20	Investigational products will be applied once daily by parent/caregiver (site staff will confirm the compliance directly or via live video chat), or by site staff (site staff will visit the participant's home as needed).
	Regimen 2	Crisaborole ointment 2% BID vs Vehicle BID	20	Investigational products will be applied twice daily by parent/caregiver (site staff will confirm the compliance directly or via live video chat), or by site staff (site staff will visit the participant's home as needed).

BID: twice daily, N: number of participants, QD: once daily

a. ages 12 years and older

b. ages 2 years to under 12 years old

### 3. ENDPOINTS AND BASELINE VARIABLES: DEFINITIONS AND CONVENTIONS

#### 3.1. Primary Endpoint(s)

- Change from baseline in TSS in target lesions treated with crisaborole ointment or vehicle on Day 15 in each regimen for each cohort for intra-participant comparison of crisaborole vs vehicle.

#### 3.2. Secondary Endpoint(s)

- Change from baseline in TSS in target lesions treated with crisaborole ointment or vehicle on Day 15 in each regimen for each cohort for inter-participant comparison of crisaborole BID vs crisaborole QD.
- Change from baseline in TSS in target lesions treated with crisaborole ointment or vehicle on Day 8 in each regimen for each cohort.
- Change from baseline in ISGA in target lesions treated with crisaborole ointment or vehicle at each visit up to Day 15 in each regimen for each cohort.
- Change from baseline in pruritus assessments in target lesions treated with crisaborole ointment or vehicle at each day up to Day 15 in each regimen using following scales:
  - Cohort 1: Peak Pruritus NRS (age  $\geq 12$ );
  - Cohort 2: Itch Severity Scale (age 6-11);

- Cohort 2: Caregiver Reported Itch Severity NRS (age 2-11).
- Incidence of TEAEs and SAEs in each regimen for each cohort.

CCI [REDACTED]

### 3.4. Baseline Variables

Demographic and baseline characteristics include:

- Age (in years);
- Sex;
- Race;
- Ethnicity;
- ISGA (global and target lesions);
- %BSA (global);
- TSS (target lesions);
- Peak pruritus NRS (target lesions) for cohort 1;
- Itch severity scale (target lesions) for cohort 2 (6 to 11 years old only);
- Caregiver reported itch severity NRS (target lesions) for cohort 2.

### 3.5. Safety Endpoints

#### 3.5.1. Adverse Events

AEs will be captured and reported in accordance with Pfizer data standards.

An AE is considered a treatment-emergent adverse event (TEAE) if the event started during the effective duration of treatment.

All events that start on or after the first dosing day and time/start time, if collected, but before the last dose plus the lag time will be flagged as TEAEs. The algorithm will not consider any events that started prior to the first dose date. If an AE starts on the same day as the first dose date, it will be considered treatment emergent unless the case report form (CRF) data indicates otherwise via explicitly recording time for AE onset and treatment dosing.

The effective duration of treatment starts at the date of the first dose of study treatment and ends at the date of the last dose of study treatment plus the lag time. An infinite lag will be used for this study.

**4. ANALYSIS SETS (POPULATIONS FOR ANALYSIS)**

Data for all participants will be assessed to determine if participants meet the criteria for inclusion in each analysis population prior to unblinding and releasing the database and classifications will be documented per standard operating procedures.

Population	Description
Full Analysis Set (FAS)	All participants randomized and receiving $\geq 1$ dose of investigational product.
Per-Protocol Analysis Set (PPAS)	All participant randomized and receiving $\geq 1$ dose of investigational product, with both baseline and Day 15 primary efficacy data, and without protocol violations that were thought to impact the efficacy evaluation during the treatment period. All protocol deviations will be reviewed and assessed by the study team prior to database release.
Safety Analysis Set	All participants receiving $\geq 1$ dose of investigational product.

**5. GENERAL METHODOLOGY AND CONVENTIONS**

The final analysis will be performed at study participant dataset release after last participant last visit.

**5.1. Hypotheses and Decision Rules**

The primary analysis in each regimen for each cohort will be a superiority test to demonstrate crisaborole ointment 2% is more efficacious than vehicle in the target lesion in participants with mild to moderate AD as measured by change from baseline in TSS between crisaborole treated lesion and vehicle treated lesion. The null hypothesis in each regimen for each cohort is that there is no difference between crisaborole ointment 2% and vehicle, and the alternative hypothesis in each regimen for each cohort is that there is difference between crisaborole ointment 2% and vehicle as measured by change from baseline in TSS at Day 15. In each regimen for each cohort the difference between crisaborole and vehicle in TSS change from baseline at Day 15 is statistically significant if  $p\text{-value} < 0.05$  (two-sided).

**5.2. General Methods**

In general, number and percentage will be presented for categorical variables. Number, mean, standard deviation, minimum, 1st, 2nd and 3rd quartiles and maximum will be presented for continuous variables.

### **5.2.1. Analyses for Binary Endpoints**

The binary endpoints will be descriptively summarized using number, percentage and 95% confidence interval (CI) of percentage at each time point.

For the intra-participant comparison of crisaborole vs vehicle in each regimen at each time point, the binary endpoints will be compared using McNemar's test. For the inter-participant comparison of regimen 1 vs regimen 2 at each time point, the binary endpoints will be compared using Chi-squared test.

### **5.2.2. Analyses for Continuous Endpoints**

The continuous endpoints will be descriptively summarized using number, mean, standard deviation, minimum, 1st, 2nd and 3rd quartiles and maximum.

For the intra-participant comparison of crisaborole vs vehicle in each regimen at each time point, a Mixed effect Models for Repeated Measures (MMRM) will be used to derive least-square mean of intra-participant difference and associated 2-sided 95% CI between crisaborole ointment 2% and corresponding vehicle. A MMRM will include the fixed effect of time point (visit or day) and an unstructured variance and covariance matrix will be used to model the dependence among the same participants across different visits up to Day 15. If there is convergence issue for unstructured variance and covariance matrix, first order autoregressive (AR(1)) variance and covariance matrix will be used.

For the inter-participant comparison of regimen 1 vs regimen 2 at each time point, a MMRM will be used to derive difference in least-square means and associated 2-sided 95% CI between regimen 1 and regimen 2. A MMRM will include the fixed effects of dosing regimen, time point (visit or day), dosing regimen-by-time point (visit or day) interaction, and baseline value of the corresponding endpoint and an unstructured variance and covariance matrix will be used to model the dependence among the same participants across different visits up to Day 15. If there is convergence issue for unstructured variance and covariance matrix, AR(1) variance and covariance matrix will be used.

### **5.2.3. Analyses for Categorical Endpoints**

Categorical endpoints will be descriptively summarized using number and percentage. Shift table from baseline to Day 8 and Day 15 will be provided.

### **5.3. Methods to Manage Missing Data**

Missing data will not be imputed for efficacy descriptive summary.

For the statistical comparison of continuous endpoints, a MMRM analysis will be conducted including only the observed data in the model under the assumption of the missing at random (MAR) for the missing mechanism.

Non responder imputation (NRI) will be used for missing values of lesion ISGA response of clear or almost clear and at least a 2 grade improvement from baseline at Day 8 and Day 15.

In addition, missing values for safety endpoints will not be imputed.

## 6. ANALYSES AND SUMMARIES

### 6.1. Primary Endpoint(s)

#### 6.1.1. Change from Baseline in TSS in Target Lesions at Day 15 (Comparison of Crisaborole vs Vehicle in Each Regimen)

##### 6.1.1.1. Main Analysis

- Estimand strategy: Hypothetical ([Section 2.1](#)).
- Analysis time point: Day 15.
- Analysis set: FAS ([Section 4](#)).
- Analysis methodology: For the intra-participant comparison of crisaborole vs vehicle in each regimen for each cohort, the intra-participant difference of change from baseline in TSS in target lesions between crisaborole and vehicle up to Day 15 will be analyzed using a MMRM that includes the fixed effect of visit specified in [Section 5.2.2](#).
- Intercurrent events and missing data: All efficacy data after discontinuation of treatment will not be considered ([Section 2.1](#)). Observed data will be included in the model, and the missing values will be handled in the model, where the values are assumed to be MAR ([Section 5.3](#)).
- Supporting objective and decision rule: Primary objective, crisaborole is superior to vehicle for the TSS change at Day 15 if the change for crisaborole is greater than for vehicle and if  $p\text{-value} < 0.05$  (two-sided).
- Reporting results:
  - Observed score: The sample size, mean, standard error (SE), standard deviation, median, Q1, Q3, minimum and maximum at baseline and post-baseline visits will be presented for each treatment.
  - Change from baseline: The sample size, mean, SE, standard deviation, median, Q1, Q3, minimum and maximum at post-baseline visits will be presented for each treatment. The least-squares mean of difference and the corresponding SE, 95% CI, p-value will be presented for all post-baseline visits.
  - Figures: 1) Line plots of the mean change ( $\pm$  SE) from baseline to Day 8 and 15 for two treatments (ie, crisaborole vs vehicle) in one figure. Figures will be developed in each regimen for each cohort, separately. In addition, 2) line plots of the mean change ( $\pm$  SE) from baseline to Day 8 and 15 for four treatments (ie, crisaborole BID vs crisaborole QD vs vehicle BID vs vehicle QD) in one figure. Figures will be developed for each cohort, separately.

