9.4.1. Efficacy Analyses

Analysis will be conducted for each cohort. The pooled analysis of cohort 1 and cohort 2 may be conducted, as appropriate. In the intra-participant comparison, a Mixed effect Models for Repeated Measures (MMRM) will be used to derive least-square means of intra-participant difference and associated 2-sided 95% confidence intervals between crisaborole ointment 2% and corresponding vehicle. In the inter-participant comparison, a MMRM will be used to derive difference in least-square means and associated 2-sided 95% confidence interval between crisaborole ointment 2% BID and crisaborole ointment 2% QD. Further details will be provided in the SAP.

Endpoint	Statistical Analysis Methods
Primary	
 The primary efficacy endpoint will be the change from baseline in TSS in target lesions treated with crisaborole ointment 2% or vehicle on Day 15. As for the intra-participant comparison between crisaborole treated lesion and the corresponding vehicle treated lesion for each regimen, and for each cohort, the intra-participant difference of change from baseline in TSS between crisaborole treated lesion and vehicle treated lesion, will be analyzed using a MMRM that includes the fixed effect of visit and an unstructured variance and covariance matrix will be used to model the dependence among the same participants across different visits up to Day 15. A MMRM analysis will be conducted including only the observed data in the model under the assumption of the missing at random (MAR) for the missing mechanism.

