#### **6.1.1.2.2. Analysis for Pooled Cohort**

The same analysis as the main analysis ([Section 6.1.1.1](#)) will be conducted for the pooled cohort of cohort 1 and cohort 2.

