## **6.2. Secondary Endpoint(s)**

### **6.2.1. Change from Baseline in TSS in Target Lesions at Day 15 (Comparison of Crisaborole BID vs Crisaborole QD)**

#### **6.2.1.1. Main Analysis**

- Estimand strategy: Hypothetical ([Section 2.1](#)).
- Analysis time point: Day 15.
- Analysis set: FAS ([Section 4](#)).
- Analysis methodology: For the inter-participant comparison of crisaborole BID vs crisaborole QD for each cohort, the change from baseline in TSS in target lesions between crisaborole BID and crisaborole QD up to Day 15 will be analyzed using a MMRM that includes the fixed effects of dosing regimen, visit, dosing regimen-by-visit interaction, and baseline value specified in [Section 5.2.2](#).
- Intercurrent events and missing data: All efficacy data after discontinuation of treatment will not be considered ([Section 2.1](#)). Observed data will be included in the model, and the missing values will be handled in the model, where the values are assumed to be MAR ([Section 5.3](#)).
- Reporting results:
  - Observed score: The sample size, mean, SE, standard deviation, median, Q1, Q3, minimum and maximum at baseline and post-baseline visits will be presented for each treatment.
  - Change from baseline: The sample size, mean, SE, standard deviation, median, Q1, Q3, minimum and maximum at post-baseline visits will be presented for each treatment. The least-squares mean and the corresponding SE, 95% CI for each treatment, the difference between the least-squares means of treatments and the corresponding SE, 95% CI, p-value will be presented for all post-baseline visits.

- Figures: Line plots of the mean change ( $\pm$  SE) from baseline to Day 8 and 15 for two treatments (ie, crisaborole BID vs crisaborole QD) in one figure. Figures will be developed for each cohort, separately.

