**6.5. Baseline and Other Summaries and Analyses**

**6.5.1. Baseline Summaries**

In each regimen for each cohort, demographic and baseline characteristics will be summarized for safety analysis set according to Pfizer data standards. Lesion baseline data will be summarized by treatment in each regimen for each cohort.

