## 9. APPENDICES

### Appendix 1. SAS Code

For the intra-participant comparison of crisaborole vs vehicle for each regimen, the following SAS code can be used for analysis of mixed model repeated measure for lesion TSS change from baseline up to Day 15 and other similar continuous endpoint shown in [Section 3](#).

```
proc mixed data=dataset;
  class subjid visit;
  model difference = visit;

  repeated visit/subject=subjid type=un;/*If there is a convergence issue
for type=un, it can be replaced by type=AR(1)*/
  lsmeans visit/cl;
run;
```

Note: difference is the intra-participant difference of change from baseline at each time point up to Day 15 between crisaborole and vehicle.

For the inter-participant comparison of crisaborole BID vs crisaborole QD, the following SAS code can be used for analysis of mixed model repeated measure for lesion TSS change from baseline up to Day 15 and other similar continuous endpoint shown in [Section 3](#).

```
proc mixed data=dataset;
  class subjid regimen visit;
  model difference = regimen visit regimen*visit baseline;

  repeated visit/subject=subjid type=un;/*If there is a convergence issue
for type=un, it can be replaced by type=AR(1)*/
  lsmeans regimen*visit/cl diff cl;
run;
```

Note: difference is change from baseline at each time point up to Day 15 of each regimen.

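### Does the primary crisaborole-versus-vehicle analysis need a version adjusted for the baseline TSS difference between the two lesions?

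*SAP*

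**What the plan says.** The Protocol (9.4.1) and the SAP (5.2.2, 6.1.1.1 and Appendix 1) agree on the crisaborole-versus-vehicle model. In the Protocol the within-participant difference of changes "will be analyzed using a MMRM that includes the fixed effect of visit and an unstructured variance and covariance matrix". In SAP 6.1.1.1 the same difference "up to Day 15 will be analyzed using a MMRM that includes the fixed effect of visit". In the SAS code this becomes "model difference = visit". SAP 5.1 states that "The primary analysis in each regimen for each cohort will be a superiority test", so there are four separate tests (two cohorts by two regimens).

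SAP 6.1.1.2 lists two supplementary analyses. One repeats the main analysis in the per-protocol set. In the other, the same analysis "will be conducted for the pooled cohort of cohort 1 and cohort 2". Neither adds a covariate, and this subsection shows no redaction.

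The BID-versus-QD comparison (SAP 6.2.1.1) uses "dosing regimen, visit, dosing regimen-by-visit interaction, and baseline value specified in" Section 5.2.2, coded as "model difference = regimen visit regimen*visit baseline". SAP 6.5.1 adds that "Lesion baseline data will be summarized by treatment in each regimen for each cohort".

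**The concern.** Three features make this look like a gap.

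- One SAP adjusts for baseline in one TSS comparison and not in the other, and the unadjusted one is primary.
- The lesions are matched on Lesion ISGA = 3 (Protocol 5.1, criterion 6), not on TSS. Two of the four TSS signs, excoriation and lichenification, do not appear in the ISGA definitions (Protocol 8.1.1 and 8.1.2). A matched pair can therefore start at different TSS values.
- A change score subtracts baseline with a coefficient fixed at 1. If more severe lesions improve more, a chance imbalance still shifts the Day 15 estimate.

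At stake would be the reading of a cell of 16 to 20 participants whose baseline table shows unequal lesions. No adjusted result would be prespecified, and one produced then would be post hoc.

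**Working it through.** **1. The plan's own figure.** Inputs from Protocol 9.2: mean within-participant difference 1.8, SD 2.2, n = 16, one-sided 0.025, paired t-test, about 20% loss.

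- Noncentrality = (1.8/2.2) × √16 = 3.27 with 15 df. Power is 86.4%, so the stated minimum of 85% holds; n = 15 gives 83.8%.
- Enrolment = 16/(1 − 0.20) = 20, as stated. Power at n = 20 is 93.4%.

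This calculation has no covariate, and neither does the planned model. With complete data, the visit-only unstructured model gives the paired mean and its usual standard error at Day 15, 2.2/√16 = 0.55.

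**2. Type I error.** The investigator fixes Lesions 1 and 2 before randomisation, and 10 participants are planned for each lesion order in each cell (Protocol 6.3.1, Table 1). The baseline difference therefore has expectation zero, and its effect on the outcome is part of the SD of 2.2. Simulation at n = 16, with correlation 0, 0.3 and 0.5 between the baseline difference and the difference in change, gave two-sided errors of 4.99%, 5.11% and 4.95%.

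**3. Effect of a chance imbalance, and of adjusting.** The documents give neither the SD of the baseline difference (SDb) nor the slope of the Day 15 change difference on it. The ranges below are assumptions.

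- Shift from a 2-SD imbalance = |slope| × 2 × SDb/√16.
- Variance explained = (slope × SDb/2.2)².
- The adjusted model fits QD and BID together, with a common slope at each visit and separate covariances, and is read at zero baseline difference. Data are complete, with assumed Day 8 SD 1.8, residual correlation 0.6 and Day 8 slope half the Day 15 slope.

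| SDb, slope | Shift (TSS points) | Variance explained | Power, visit-only | Power, adjusted |
|---|---|---|---|---|
| uninformative | 0 | 0 | .865 | .850–.853 |
| 0.5, −0.5 | 0.125 | 1.3% | .866–.869 | .856–.862 |
| 0.5, −0.7 | 0.175 | 2.5% | .861–.865 | .856–.860 |
| 1.0, −0.5 | 0.25 | 5.2% | .865 | .867–.872 |
| 1.0, −0.7 | 0.35 | 10.1% | .863–.864 | .882–.887 |
| 1.5, −0.5 | 0.375 | 11.6% | .866–.867 | .890–.893 |
| 1.5, −0.7 | 0.525 | 22.8% | .863–.865 | .924–.928 |

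Given a 2-SD imbalance, the visit-only two-sided error is .054, .068, .080 and .117 for (0.5, −0.5), (1, −0.5), (1, −0.7) and (1.5, −0.7). An imbalance beyond 2 SD has probability 1 − 0.9545 = 4.55% in a cell. Averaged over all randomisations, the error returns to the 5% of step 2.

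The chance of at least one such cell is 1 − 0.9545⁴ = 17.0%. That figure is the same for any covariate, whatever its SD, in any trial with four independent cells. It says nothing about whether the imbalance matters.

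**4. Adjusting each cell separately.** This matches how the primary tests are run. At n = 16, power is 83.5% at correlation 0, 85.0% at 0.2, 86.7% at 0.3 and 92.2% at 0.5, against about 86.4% unadjusted. Break-even is near 0.3, about 9% of variance. The shared-slope model breaks even at about 4%, because it borrows the slope across regimens that the plan analyses apart. The mean estimate is about 1.80 in size with or without adjustment.

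**5. Sensitivity to the adjusted model's details.** The power figures in step 3 use 14 and 15 df. If 29 df were used for a statistic that behaves like 14 to 15 df, the two-sided error would be about 0.06. Pooling the residual variance across regimens, with assumed SDs of 1.6 and 2.7, gives .103–.118 in the more variable regimen. Adjustment brings choices of its own that the visit-only model avoids.

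**6. The two models side by side.** In BID versus QD, the lesions belong to different people, whose starting TSS can differ widely. In crisaborole versus vehicle, both lesions belong to one person, and anything common to the pair cancels in the difference. The covariates would also differ: one lesion's baseline in the former, a difference of two baselines in the latter. A baseline term in one does not imply that the other lacks one.

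**The case for a change.** The best case for the concern is that the facts behind it are right. ISGA matching does not equalise TSS, and randomisation balances on average rather than in each cell. The change score does not remove dependence on baseline when the slope is not zero. SAP 6.5.1 will put any imbalance on view. A supportive analysis would use data already collected, would leave the primary model alone, and has prespecification value only if written before unblinding.

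All of that stands as a reason why a sponsor might choose to add the analysis. It does not show that the plan goes wrong without it. An added analysis with no success rule would change neither the primary estimate nor its decision rule. Regimen selection for the next phase is tied to the descriptive BID-versus-QD comparison (Protocol 2.1 and 4.3), whose model already includes baseline.

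The larger effects (a shift of 0.525, conditional error of .117, power of about .93) all need SDb = 1.5. Under normality, that means about 32% of participants have ISGA-matched lesions more than 1.5 TSS points apart. The design works against this: the lesions must be of equal severity, and bilateral sites are preferred. At SDb = 0.5, the shift is at most 0.175 against a standard error of 0.55, and adjustment slightly lowers power.

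**Conclusion.** The concern does not hold. The visit-only model is stated consistently in both documents, matches the sample-size calculation, keeps its two-sided size at about 5% and has 86.4% power at n = 16. Leaving out a baseline-difference covariate creates no bias, contradiction or missing decision rule.

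Adjusting would change power at n = 16 by about −1 to +6 points with a slope shared across regimens (assumed SDb 0.5–1.5, slope −0.5 to −0.7, or no relation). Cell by cell, it would change power by about −3 to +9 points (assumed correlation 0 to 0.6). The sign depends on quantities the documents do not supply.

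The conclusion rests on product being randomised to pre-labelled lesions and on the planning SD of 2.2. The simulations use complete data, while the plan allows for about 20% non-compliance or discontinuation. Redacted text elsewhere in the documents cannot be judged and is not needed for this conclusion.
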